## 7.4 Classification of Responder Status

A desensitization responder is defined as a subject who achieves a desensitization response as determined by tolerating at least 300 mg (443 mg cumulative) of peanut protein (measured as 600 mg of peanut flour) at the Exit DBPCFC with no more than mild symptoms.

A non-responder is an escalation failure or a subject who experienced dose-limiting symptoms (moderate or worse) at or before the 300 mg dose of peanut protein during the Exit DBPCFC.

Additional classification of responder and non-responder categories are provided in Table 7.2.

Response	Response	Criteria	
Category	Subcategory [1]		
Desensitization Responder	Passed Exit DBPCFC	Tolerate at least 300 mg (443 mg cumulative) of peanut protein at the Exit DBPCFC with no more than mild symptoms	
	Ad libitum peanut consumption	Added ad libitum peanut consumption to their diet	
Non-Responder	Failed Exit DBPCFC	Fail to tolerate at least 300 mg (443 mg cumulative) of peanut protein at the Exit DBPCFC with no more than mild symptoms	
Reached 300 Reason		Reasons [2] include:	
	mg/day but Exit DBPCFC was not conducted	
 
Eligible for DBPCFC but it was not conducted due to at least one treatment-related reason, as entered on the eCRF
 
Eligible for DBPCFC but it was not conducted
 
	
		only for reasons unrelated to treatment, as entered on the eCRF	
	Escalation Failure	Fail to achieve the target maintenance study product dose of at least 300 mg and thus did not qualify for the Exit DBPCFC. Reasons[3] include:	
		
 
Discontinued as an escalation failure during initial escalation (Visit 01)
 
	
		
 
Discontinued as an escalation failure during up- dosing prior to Week 24
 
	
		
 
Discontinued as an escalation failure after Week 24
 
	
		Discontinued for treatment-related AE or death	
		
 
Discontinued for other reasons related to treatment
 
	
		Discontinued for reasons unrelated to treatment	

Table 7.2 Response Categories

[1] Subjects will be assigned to only one response subcategory during blinded data review.

[2] More than one reason may be given for the DBPCFC not being conducted for a subject who reached the 300 mg/day target. Each reason will be classified as treatment-related, or not, during blinded data review.

[3] More than one reason for discontinuation may be given. Each discontinuation reason will be classified as treatment-related, or not, during blinded data review. Escalation failure is a specific reason for early discontinuation on the eCRF.

## 7.5 Data Derivations and Definitions

The following definitions and derivations will be used throughout this study:

- Study Day is calculated as (assessment date first dose date + 1) for assessments and visits performed on or after the first dose date, and (assessment date – first dose date) for assessments and visits prior to the first dose date.
- Baseline is defined as the last non-missing value prior to the first dose of randomized study treatment.
- Change from baseline is calculated as observed value after the first dose baseline value.
- The active treatment period is defined as the time period beginning with the date and time of the first dose of randomized study product, and ending with the date of the last dose of randomized study product taken prior to Exit DBPCFC.

## 7.6 Data Pooling

Data pooling will be performed as necessary for exploratory analyses, as described in Section 9.5. No other data pooling is planned.

#### 7.7 Maintenance of the Study Blind Prior to Database Lock

Due to the nature of the study, some data will be suggestive of randomized treatment assignment (specifically: allergy symptoms during dosing; Exit DBPCFC results; and adverse events, anaphylaxis episodes, concomitant medications and therapies, and IgG4 & IgE lab results after the first dose of randomized study treatment). The following procedures will be implemented to assist in maintaining the study blind among project team members during blinded data reviews prior to database lock (see also Section12):

- All tables and figures will be produced using surrogate randomization.
- All listings will have subject numbers masked by a randomly created subject identifier, which will be the same for each subject across listings. Listings may also include the surrogate randomized treatment used in the tables.

Although the study statistician and programming team does not have access to treatment assignments, they do have access to the actual subject identifiers and safety and efficacy data potentially suggestive of treatment assignment on a subject level basis. As a precaution, all advice by the lead statistician regarding study conduct issues will be documented. If a conflict arises, the lead study statistician will inform the project team, and if appropriate, the sponsor statistician and/or another statistician will be designated for this task. The study statistician

may attend decision-making meetings (see Section 12) to provide information as requested, but will not be involved in the decisions.

The sponsor statistician will not have access to the ARC002 treatment assignments (directly based on ARC001 treatment assignments) for subjects who roll over into ARC002. Similarly, the sponsor statistician will not have access to listings with actual subject identifiers or treatment information, and will not have access to the TEMPO database to view data directly. The sponsor statistician will receive subject listings, with surrogate and masked information as described above. The sponsor statistician will remain thusly blinded, in order to contribute to unbiased decisions made by the sponsor (see Section 12).

Other sponsor representatives have access to subject tracking information, e.g., the dates of up-dosing visits, and will have access to ARC002 treatment assignments upon subject enrollment in that study, that, if combined, could be suggestive of treatment assignment on a subject level basis. These sponsor representatives may, however, still review blinded tables, with surrogate treatment information. Sponsor representatives involved in the pre-database lock blinded data review will only have access to a limited number of masked listings for conducting that blinded review (see Section 12). Additionally, the sponsor medical monitor and other sponsor representatives will have access to the masked listings described below in Table 7.3 for the purpose of ongoing safety review during the conduct of the study.

Output ID / Title	Frequency
LO1 Adverse Events	Monthly
LO2 Concomitant Medications: Epinephrine Rescue Medications	Monthly

#### 7.8 Randomization, Treatment Assignments, and Blinding

Subjects are randomized in a 1:1 ratio to each study treatment (CPNA or placebo) using the TEMPO system. A central randomization schedule of randomly permuted blocks was prepared by an independent unblinded statistician for use in the TEMPO system.

Subjects will be unblinded after the final visit is completed and they exit the ARC001 trial. Subjects who withdraw and do not complete their final visit assessments will be unblinded after they exit from the study. End of study (scheduled) unblinding will be requested by the site. Emergency (unscheduled) unblinding for safety reasons may also occur, as described in the protocol. Emergency unblinding may be requested by the site or other study team members (such as the medical monitor).

For either type of unblinding, the date of unblinding, type (scheduled or unscheduled), and person who requested the unblinding will be processed and documented in TEMPO. The actual treatment assignment will be made available only to the person requesting unblinding. Other study team personnel will receive notification that the treatment assignment has been provided, but will not be notified of the actual treatment assignment.

Masking procedures for outputs provided only to the Data Monitoring Committee (DMC) are described in the DMC Charter.

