All subjects who reach and tolerate 300 mg/day for 2 weeks will undergo an exit DBPCFC. Those unable to achieve a dose of 300 mg/day of peanut protein by 34 weeks will be considered escalation failures and will not undergo an exit DBPCFC.

During the treatment period, the subjects will be monitored for tolerability as illustrated in Figure 6–1 and Figure 6–2 (see Section 6.8.4).

If a subject is removed from therapy because of failing escalation during the initial escalation period (Visit 1; Days 1 to 3), the subject will be followed for safety and asked to return to the Clinical Research Center 14 days following their last dose of study product to undergo an Early Discontinuation Visit (see Section 6.5).

If a subject's up-dosing is halted because of failing subsequent build-up (i.e., after the initial escalation period; Visit 1), the subject will continue to be dosed at the last tolerated dose level and to be followed for safety biweekly (following their established visit schedule) until Week 24, i.e., a maintenance phase (See also Section 6.8.4). Dosing will be stopped after the Week 24 Visit; and the subject will be asked to return to the Clinical Research Center 14 days following their last dose of study product to undergo an Early Discontinuation Visit (see Section 6.5).

For subjects who halt dose-escalation after Week 24, there will be no maintenance phase. Dosing in these subjects will be discontinued when dose-escalation is stopped. They will be followed for safety and asked to return to the Clinical Research Center 14 days following their last dose of study product to undergo an Early Discontinuation Visit (see Section 6.5).

For subjects who achieve the targeted dose of 300 mg/d by Week 34, the maintenance phase comprises the last two weeks of the study.

Subjects who prematurely discontinue treatment before Week 24 for any reason will be brought in for an early discontinuation visit 14 days after their last dose.

A Data Monitoring Committee (DMC) has been established and will meet every 3 months to monitor the study for safety.

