3.3 Exit DBPCFC

All subjects who reach the targeted daily dose of 300 mg/day and maintain that dose for 2 weeks will undergo an exit DBPCFC. The exit DBPCFC will be performed in accordance with PRACTALL guidelines, but requiring progression in an unaltered sequence (Table 6-2), without repeating any dose.

Each subject will be unblinded after he/she completes the DBPCFC.

Subjects who do not reach the target dose by Week 34 are not eligible for the exit DBPCFC, and will be considered escalation failures. They will be unblinded no sooner than Week 24.

All placebo subjects are eligible for rollover into ARC002. Placebo subjects enrolled in ARC002 will undergo an escalation schedule identical to that for active subjects in the ARC001 protocol. All subjects on active treatment who pass the DBPCFC are eligible to proceed to ARC002. Subjects in the active treatment group who do not pass the DBPCFC at the 300 mg (443 mg cumulative) protein level will be considered endpoint failures and will not be eligible for rollover into the ARC002 protocol.

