4.3.1 Criteria

No subject randomized into this trial who discontinues treatment for any reason will be replaced.

Unless required for safety reasons (i.e., medical treatment of SAEs), subjects eligible for an exit DBPCFC will not be unblinded earlier than their scheduled DBPCFC. Subjects who are considered escalation failures will be unblinded no sooner than Week 24.

Any subject may be prematurely terminated from additional allergen exposures for the following reasons:

- Life-threatening symptoms (CoFAR Grade 4; refer to Table A4-3 in Appendix 4), including, but not limited to, anaphylaxis resulting in hypotension, neurological compromise, or mechanical ventilation secondary to peanut OIT dosing or any peanut food challenge
- 2. Severe symptoms (CoFAR Grade 3; refer to **Table A4-3** in **Appendix 4**), including, but not limited to, those that require aggressive therapy (to be determined by the investigator, but may include such interventions as IV epinephrine, intubation, or admission to an intensive care unit) or those that are recurrent
- 3. Poor control or persistent activation of secondary atopic disease (e.g., atopic dermatitis, asthma)
- 4. Started on ARBs, ACE, beta-blockers, or other prohibited medications, with no alternative medications available per the prescribing doctor

- 5. Pregnancy
- 6. Circumstances (e.g., concurrent illness, such as gastroenteritis) requiring missed peanut OIT maintenance dosing of > 7 consecutive days
- Non-adherence with home peanut OIT dosing protocol (excessive missed days; i.e., > 3 consecutive days missed on 3 or more occasions) would be a safety issue warranting discontinuation

Any subject may also be prematurely terminated from the study if:

- 8. The subject elects to withdraw consent from all future study activities, including follow-up.
- 9. The subject is "lost to follow-up" (i.e., no further follow-up is possible because attempts to reestablish contact with the subject have failed).
- 10. The subject develops biopsy-documented eosinophilic esophagitis (EoE).
- 11. The subject's continued participation in the study is assessed by the investigator to constitute a threat to the safety of the subject or the safe conduct of the study
- 12. The subject dies (CoFAR Grade 5)

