6.5 Visit 03 - Exit Visit / Early Discontinuation Visit

Subjects who tolerate 300 mg/day and are maintained at this dose for 2 weeks will return to the clinic for an Exit visit. For these subjects, the Exit visit will occur at approximately 6-9 months post-Visit 01.
Subjects who fail escalation or build-up, or who prematurely discontinue treatment, will return to the site for an Early Discontinuation visit that consists of the same procedures as the Exit visit, but without a DBPCFC or associated optional blood draws. An Early Discontinuation visit is to occur 14 days from the last dose of study product.

The following procedures will be performed at the Exit visit:

- Medical/allergy history
- Concomitant medications
- Physical exam, including weight and height
- Vital signs (blood pressure, pulse rate, body temperature)
- PEFR (3 attempts are to be performed, and the best value taken). PEFR should be measured at the same time for each visit assessment.
- Urine pregnancy test, for females of childbearing potential
- Diet history
- Blood draw for peanut-specific IgE and IgG4 measurement (mechanistic assays), the amount to be specified by local laboratory guidelines.
- Optional blood draw (pre-DBPCFC) for exploratory analysis by ITN. The amount taken should be 5 mL/kg in children weighing ≥30 kg, with a maximum of 60 mL in total. Blood draw should be collected per NIH guidelines.
- Skin prick test to peanut extract
- Physician global assessment of disease activity using a 100-mm VAS
- Monitoring for compliance and allergic symptoms

In addition to the procedures listed above, eligible subjects will have an exit DBPCFC performed. Eligible subjects are those who tolerate 300 mg/day and are maintained at this dose for 2 weeks.

For placebo subjects only:

• Exit DBPCFC conducted in accordance with PRACTALL guidelines as described in Section 6.6.2, then proceed to ARC002

For active-treatment subjects completing DBPCFC only:

• Proceed to ARC002

Each subject participating in the study will be unblinded when he/she completes the Exit visit procedures (including the exit DBPCFC for eligible subjects).

6.6 Double-Blind, Placebo Controlled Food Challenge (DBPCFC) in accordance with PRACTALL guidelines

The DBPCFC is performed by feeding gradually increasing amounts of the suspected food under physician observation.^{25,26} A sample of food challenge from the PRACTALL guidelines using peanut flour is given in Table 6-1.

Challenge Doses				

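### The documents give conflicting unblinding times for escalation failures: SAP 7.8 omits the protocol's Week 24 floor, by up to about 22 weeks for a Visit 01 failure

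*SAP*

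**What the plan says.** Five places set the time of scheduled unblinding for a subject who does not reach the target dose.

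- Protocol 4.3.1: "Subjects who are considered escalation failures will be unblinded no sooner than Week 24".
- Protocol 3.3 says the same of subjects who miss the target dose by Week 34: "They will be unblinded no sooner than Week 24".
- Protocol 6.5: "Each subject participating in the study will be unblinded when he/she completes the Exit visit procedures". The section covers the Exit and the Early Discontinuation visit together, and the sentence goes on to mention the DBPCFC for eligible subjects only, so it also reaches subjects who have no challenge.
- Protocol 6.13 ends the double-blind at completion of the exit DBPCFC, at escalation failure or at endpoint failure. It then gives Week 34 for subjects not eligible for the DBPCFC.
- SAP 7.8: "Subjects will be unblinded after the final visit is completed and they exit the ARC001 trial". For those who miss the final visit: "Subjects who withdraw and do not complete their final visit assessments will be unblinded after they exit from the study".

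The final visit for an early leaver is fixed by Protocol 6.5: "An Early Discontinuation visit is to occur 14 days from the last dose of study product". On what follows, Protocol 3.3 says: "All placebo subjects are eligible for rollover into ARC002". SAP 7.8 has the site request end-of-study unblinding, and the assignment is shown to the requester only.

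**The concern.** A site that follows SAP 7.8 or Protocol 6.5 can unblind an early escalation failure at a time that Protocol 3.3 and 4.3.1 forbid. A site that follows 6.13 could act on the day of failure or wait until Week 34. The documents do not say which rule governs.

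Two things are at stake. First, site staff learn individual assignments while other subjects at the same site are still being dosed and challenged. The primary endpoint depends on the investigator's judgment of symptom severity and tolerability (SAP 7.3), and SAP 7.7 accepts that dosing symptoms and similar data can suggest the arm. Second, without a floor, leaving early is a way to learn the arm. Because every placebo subject is eligible for ARC002, where placebo subjects follow the active escalation schedule, a subject who suspects placebo has some reason to leave. Leavers count as non-responders (Protocol 9.1.1, SAP 7.3), so exits of that kind would lower the placebo response rate.

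**Working it through.** The documents give no figure for early unblinding other than the Week 24 floor, so there is no planned figure to reproduce. The check is one of dates.

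**Inputs**

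- Earliest escalation failure: Visit 01, Days 1 to 3 (Protocol 3.2).
- Final visit for a leaver: last dose + 14 days (Protocol 6.5).
- Floor: Week 24 (Protocol 3.3, 4.3.1). Counting from Day 1 of Visit 01, this is Day 168 (24 × 7) or Day 169 (Day 1 + 168).
- Build-up failures before Week 24: dosed at the last tolerated level to Week 24, then a final visit 14 days later (Protocol 3.2, 6.8.4).

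**Visit 01 failure**

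Final visit = Day 1 + 14 = Day 15, up to Day 3 + 14 = Day 17. Gap to the floor = (floor day − final visit day) / 7:

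- longest: (169 − 15) / 7 = 22.0 weeks
- shortest: (168 − 17) / 7 = 21.6 weeks

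**Other discontinuations**

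For a last dose at Week *w*, the final visit is at Week *w* + 2, so the gap is 24 − (*w* + 2) = 22 − *w* weeks.

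| Last dose | Final visit | Gap to Week 24 |
|---|---|---|
| Week 4 | Week 6 | 18 weeks |
| Week 12 | Week 14 | 10 weeks |
| Week 20 | Week 22 | 2 weeks |
| Week 22 | Week 24 | 0 |
| Week 24 (build-up failure kept on dose) | Week 26 | none; 2 weeks after the floor |

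A withdrawal who misses the final visit is unblinded after exit under SAP 7.8. The documents do not tie exit to a day, so no gap can be computed for that group.

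**Who the floor covers**

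The protocol writes the floor for escalation failures and, in 3.2 and 6.5, mentions premature discontinuation separately. SAP 7.3 defines an escalation failure as a subject who misses 300 mg/day by Week 34 or does not complete two weeks on it. SAP Table 7.1 places discontinuations before the target dose in that class, including those unrelated to treatment. With that definition the floor reaches most early leavers. Subjects who reached 300 mg/day, were eligible for the DBPCFC and did not have it are a separate category in SAP Tables 7.1 and 7.2, and the floor in 3.3 and 4.3.1 does not cover them.

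**The same Visit 01 failure under each rule**

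| Source | Time of unblinding |
|---|---|
| Protocol 6.13, blind ends at escalation failure | Day 1 to 3 |
| SAP 7.8 and Protocol 6.5 | from about Day 15 to 17 |
| Protocol 3.3 and 4.3.1 | Week 24 or later |
| Protocol 6.13, not eligible for the DBPCFC | Week 34 |

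**Effect on the subject's own outcome**

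A subject without an Exit DBPCFC is a non-responder whenever unblinded, apart from the documented ad libitum peanut exception in SAP 7.3. Adding the floor therefore leaves sample size, alpha and the coding of that subject unchanged.

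**The case against.** The strongest reply is that this is a small inconsistency with little reach.

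- SAP 7.8 says after the final visit and exit, which sets an earliest point and can coexist with a later floor. SAP 1 also refers the reader to the protocol for study conduct. This stands as a possible reading. It does not settle the matter, because Protocol 6.5 ties unblinding to completion of the visit, and 6.13 gives other dates again.
- The 22-week gap and the incentive to leave describe different people. Visit 01 failures are removed because they did not tolerate the initial doses. A symptom-free subject who guesses placebo would leave later, with a smaller gap. This stands, and 22 weeks must be read as a maximum.
- A reader might infer that a placebo leaver could start active product about 22 weeks early. The documents do not support that. They give eligibility for ARC002 but no entry date. The Synopsis places ARC002 after completion of ARC001, and Protocol 6.5 describes placebo subjects going on to it after their exit challenge.
- A reader might also infer a material rise in type I error. Take 25 per arm, a 25% pass rate in both arms and the SAP 9.1 test. The chance of a significant result favouring CPNA is 2.6% with no leavers. It is 4.2% or 5.8% if 3 or 5 placebo subjects, and no CPNA subjects, become fixed non-responders. Those figures rest on a hypothetical one-sided loss. The plan assumes equal loss of 3 or 5 per arm, and 3 extra placebo leavers on top of that give 3.7% or 3.2%. Nothing in the documents supports any particular number of such leavers, and 25% is itself stated as an upper limit.
- Sites learn assignments in any case as each completer is unblinded after the challenge. This also stands: the floor removes only the additional, earlier disclosures.
- The mITT, PP and Completer analyses would help to show differential early exit. They help with detection, but they do not restore a blind that has been broken.

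**Conclusion.** The conflict is real and should be corrected. SAP 7.8 and Protocol 6.5 omit a floor that Protocol 3.3 and 4.3.1 both state, and Protocol 6.13 disagrees with both sets. The size is up to about 22 weeks, for Visit 01 failures only. For later discontinuations it is 22 minus the week of last dose, and it is nil from Week 22 and for build-up failures kept on dose to Week 24. Applying the floor to discontinuations other than Visit 01 and build-up failures rests on the SAP 7.3 definition of escalation failure.

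The consequence is a risk to the blind at site level and an avoidable incentive to leave. It is not a demonstrated bias in the primary result. How many subjects would be affected is unknown, and the documents give no basis for an estimate.

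**What to change.** Reconcile Protocol 3.3, 4.3.1, 6.5 and 6.13 with SAP 7.8 so that they carry one rule: scheduled unblinding of any subject classed as an escalation failure, including early discontinuations so classed under SAP 7.3, occurs at the later of the final visit (or exit, if that visit is missed) and Week 24 after Visit 01.

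- In 6.13, remove the implication that the blind ends at the moment of escalation failure, and align the Week 34 sentence with the rule. For a subject dosed to Week 34 the final visit falls at about Week 36 (34 + 2).
- State separately which rule applies to subjects who reached 300 mg/day, were eligible and had no DBPCFC, since 3.3 and 4.3.1 do not cover them.
- Set TEMPO to refuse scheduled requests before the permitted date. Leave emergency unblinding as it is.

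The cost is wording in two documents and one date check in TEMPO. The drawback is that early leavers wait longer to learn their assignment, by up to about 22 weeks for a Visit 01 failure.
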